5.5.5 Blinding

5.5.5.1 Blinding of Investigational Product

All AbbVie personnel with direct oversight conduct and management of the trial (with the exception of AbbVie Clinical Drug Supply Management and AbbVie Pharmacovigilance Team), the Investigator, the study site personnel, and the subject will remain blinded to each subject's treatment with venetoclax/placebo throughout the course of the study.

All subjects will be treated with open-label LDAC.

The IRT system can provide access to blinded subject treatment information during the study. AbbVie must then be notified within 24 hours of the blind being broken. The date and reason that the blind was broken must be recorded in the source documentation and eCRF, as applicable.

Following the final analysis results, the Investigator, the study site personnel, the subjects, and AbbVie personnel will be unblinded by the Sponsor to subjects' treatment assignment.

5.5.5.2 Blinding of Data for Independent Data Monitoring Committee (IDMC)

An IDMC will review safety and efficacy data for this study in an un-blinded fashion and provide recommendations to AbbVie as per the IDMC charter. Details of the IDMC, including IDMC membership, which will include individuals with experience in treatment of patients with AML, and member responsibilities, will be outlined in the IDMC Charter. Aggregate clinical safety data will be reviewed on a real-time basis throughout the course of the study.

5.5.6 Treatment Compliance

The investigator or his/her designated and qualified representatives will dispense study drug only to subjects enrolled in the study in accordance with the protocol. The study drug must not be used for reasons other than that described in the protocol.

An interactive response system (IRT) will assign every bottle and/or kit of venetoclax/placebo and AbbVie supplied LDAC to be dispensed to a subject during the study. Prior to each scheduled visit, site personnel must contact IRT for the next bottle or kit number(s) assignment. AbbVie or its designee will provide specific instructions on the use of IRT.

To document compliance with the treatment regimen, subjects will be instructed to return all unused tablets and/or bottles (even if empty) and any other study-related items, such as study treatment diaries, as necessary to the study coordinator at scheduled study visits. Compliance will be monitored and documented by the designated study site personnel on

the appropriate form. The designated study site personnel will question the subject regarding adherence to the dosing regimen, record the number of tablets and/or bottles returned, the date returned and determine treatment compliance before dispensing new study drug to the subject. Compliance below 80% may require counseling of the subject by study site personnel.

5.5.7 Drug Accountability

The investigator or his/her representative will verify that study drug supplies are received intact and in the correct amounts. This will be documented by signing and dating the Proof of Receipt or similar document. The investigator or his/her designated representatives will administer study drug only to subjects enrolled in the study. A current (running) and accurate inventory of study drug will be kept by the investigator and will include shipping invoices and the date on which study drug is dispensed to the subject. An overall accountability of the study drug will be performed and verified by the AbbVie monitor throughout the study and at the study site closeout visit. Upon completion or termination of the study, all original containers (containing partially used or unused venetoclax/placebo) will be returned to AbbVie according to instructions from AbbVie or the designated monitor(s). If pre-arranged between AbbVie and the site, destruction of used and unused venetoclax or placebo bottles will be performed at the site. Empty containers will be destroyed at the site. Labels must remain attached to the containers.

5.6 Discussion and Justification of Study Design

5.6.1 Discussion of Study Design and Choice of Control Groups

This is a multicenter, randomized, double blind study to evaluate the efficacy and safety of venetoclax plus LDAC compared to an active control of placebo plus LDAC. The choice of the control group allows for a double blind assessment of the contribution of venetoclax to the safety and efficacy of the backbone regimen LDAC.

LDAC is a standard treatment option in many countries worldwide and is often referred to as low intensity therapy for AML. Low intensity therapy, such as LDAC, azacitidine, or decitabine are considered appropriate treatment approaches by the National Cooperative Cancer Network (NCCN)²⁶ and European LeukemiaNet (ELN)²⁸ for patients who are not candidates for intensive chemotherapy induction or HSCT. Two Phase 3 trials have compared azacitidine²⁹ and decitabine³⁰ to physician's choice therapy for older patients with newly diagnosed AML to evaluate if either provided a statistically significantly longer survival when given as the initial treatment for AML. To date, neither agent has been found to provide a significantly longer survival for patients with newly diagnosed AML than for those randomized to physician choice. The most common treatment, in both studies, amongst the patients randomized to physician choice was LDAC. The response rates to LDAC when administered as monotherapy are substantially lower than what is seen in Study M14-387 in combination with venetoclax and preliminary projections for median survival times also appear better than for the aforementioned historical experiences with LDAC monotherapy.³¹

5.6.2 Appropriateness of Measurements

Standard pharmacokinetic, statistical, clinical and laboratory procedures will be utilized in this study. The efficacy measurements in this study are standard and validated.

The PRO measures chosen for this study have been validated in cancer patients and include a generic HRQoL measure (EQ-5D-5L), a cancer-specific HRQoL measure that includes functional and symptom scales as well as a global health status scale (EORTC QLQ-C30), and a symptom-based measure to assess fatigue (PROMIS Fatigue SF 7a). The specific symptoms and functional aspects assessed by these measures are considered to be among the most impactful to AML patients.^{32,33}

5.6.3 Suitability of Subject Population

Subjects who have histological confirmation of acute myeloid leukemia who are treatment naïve, greater than or equal to 18 years of age, considered ineligible for treatment with a standard induction regimen due to age and comorbidity, and appropriate for LDAC

control arm may be enrolled. Study M14-387, which provides the experimental arm projections, enrolled a similar patient population.

5.6.4 Selection of Doses in the Study

The selected dosage of venetoclax is based on the results from Study M14-387, an ongoing Phase 1b/2 study of escalating doses of venetoclax in combination with LDAC in treatment naïve AML subjects greater than or equal to 65 years of age, and ineligible for treatment with a standard cytarabine and anthracycline induction regimen. In the dose escalation phase, LDAC was administered subcutaneously at 20 mg/m² QD on Days 1 – 10 of each 28-day cycle of therapy. Venetoclax began on Day 2, to allow PK assessments of monotherapy LDAC of Cycle 1 followed by a ramp up to continuous daily dosing at the designated doses of 600 mg for Cohort 1 and 800 mg for Cohort 2.

Eighteen subjects were enrolled in the Phase 1 dose escalation portion (10 subjects at the 800 mg dose and 8 subjects at 600 mg dose) and an additional 53 subjects were enrolled in the Phase 2 portion of the study at the 600 mg dose. Two of the 10 subjects enrolled to the 800 mg venetoclax cohort with LDAC experienced a dose-limiting toxicity identifying 600 mg venetoclax as the maximum tolerated dose (MTD) in co-administration with LDAC.

An exposure-response analysis was conducted across the 71 enrolled subjects to establish the relationship between venetoclax exposure and response rates to support venetoclax dose selection in Study M16-043.

In summary, based on the preliminary results of exposure-response analysis and the observed tolerability data, the 600 mg dose of venetoclax in combination with LDAC was selected to maximize the response rates while avoiding dose-limiting toxicities.

5.6.4.1 Dose Adjustments for Venetoclax Upon Co-Administration with Anti-Fungal Agents

Patients with AML are at high risk for febrile neutropenia and life threatening fungal infections. Azole agents, all of which are CYP3A inhibitors, are widely used in these patients for prophylaxis and treatment of invasive fungal infections. As venetoclax is predominantly metabolized by CYP3A, co-administration with antifungal agents which are strong or moderate CYP3A inhibitors will increase venetoclax exposures.

The effect of two strong CYP3A inhibitors (posaconazole and ketoconazole) on the pharmacokinetics of venetoclax was evaluated in two separate studies. Study M13-364 was conducted to evaluate the effect of ketoconazole given once daily on pharmacokinetics of single dose of venetoclax in 12 subjects with NHL³⁴ and a cohort of 12 untreated elderly AML subjects in Study M14-358 was enrolled to assess the effect of posaconazole given twice daily on exposures of venetoclax given once daily.³⁵ Furthermore, prior studies indicated venetoclax bioavailability to be dependent on both food and dose. To account for the effect of covariates such as food and dose non-linearity on the bioavailability of venetoclax, a population PK model was used to simulate exposures of venetoclax in presence of strong CYP3A inhibitors.

The ramp-up scheme for venetoclax when given alone is 100 mg on Day 1, 200 mg on Day 2, 400 mg on Day 3 and 600 mg QD from Day 4 onwards. To match the exposures (AUC) from these doses, venetoclax doses of 10 mg on Day 1, 20 mg on Day 2 and 50 mg QD from Day 3 onwards were chosen when co-administered with strong CYP3A

inhibitors to mitigate any possible risk for TLS and ensure safety. Predicted venetoclax exposures when administered alone and in presence of strong CYP3A inhibitors at the recommended dose reductions are shown in [Table 6](#).

6.0 Complaints

A complaint is any written, electronic, or oral communication that alleges deficiencies related to the physical characteristics, identity, quality, purity, potency, durability, reliability, safety, effectiveness, or performance of a product/device after it is released for distribution. The investigational product in this study is defined as venetoclax, LDAC or placebo.

Complaints associated with any component of this investigational product must be reported to the Sponsor (Section [6.2.2](#)). For AEs, please refer to Sections [6.1](#) through [6.1.7.1](#). For product complaints, please refer to Section [6.2](#).

6.1 Medical Complaints

The investigator will monitor each subject for clinical and laboratory evidence of adverse events on a routine basis throughout the study. The investigator will assess and record any adverse event in detail including the date of onset, event diagnosis (if known) or sign/symptom, severity, time course (end date, ongoing, intermittent), relationship of the adverse event to study drug, and any action(s) taken. For serious adverse events

considered as having "no reasonable possibility" of being associated with study drug, the investigator will provide an alternative cause of the event. For adverse events to be considered intermittent, the events must be of similar nature and severity. Adverse events, whether in response to a query, observed by site personnel, or reported spontaneously by the subject will be recorded.

All adverse events will be followed to a satisfactory conclusion.

6.1.1 Definitions

6.1.1.1 Adverse Events

An adverse event is defined as any untoward medical occurrence in a patient or clinical investigation subject administered a pharmaceutical product and which does not necessarily have a causal relationship with this treatment. An adverse event can therefore be any unfavorable and unintended sign (including an abnormal laboratory finding), symptom, or disease temporally associated with the use of a medicinal (investigational) product, whether or not the event is considered causally related to the use of the product.

Such an event can result from use of the drug as stipulated in the protocol or labeling, as well as from accidental or intentional overdose, drug abuse, or drug withdrawal. Any worsening of a pre-existing condition or illness is considered an adverse event.

Worsening in severity of a reported adverse event should be reported as a new adverse event. Laboratory abnormalities and changes in vital signs are considered to be adverse events only if they result in discontinuation from the study, necessitate therapeutic medical intervention, meet protocol specific criteria (see Section 6.1.7) regarding toxicity management and/or if the Investigator considers them to be adverse events.

Hospitalization of a subject to allow observation and management (e.g., for IV hydration) for the purpose of TLS prophylaxis will not be captured as a serious adverse event (SAE), unless there is an additional reason for hospitalization or an additional criterion for seriousness other than hospitalization.

An elective surgery/procedure scheduled to occur during a study will not be considered an adverse event if the surgery/procedure is being performed for a pre-existing condition and the surgery/procedure has been pre-planned prior to study entry. However, if the pre-existing condition deteriorates unexpectedly during the study (e.g., surgery performed earlier than planned), then the deterioration of the condition for which the elective surgery/procedure is being done will be considered an adverse event.

A treatment-emergent adverse event is defined as any adverse event with onset or worsening reported by a subject from the time that the first dose of venetoclax/placebo or LDAC is administered until 30 days have elapsed following discontinuation of venetoclax/placebo and LDAC administration.

6.1.1.2 Serious Adverse Events

If an adverse event meets any of the following criteria, it is to be reported to AbbVie as a serious adverse event **within 24 hours** of the site being made aware of the serious adverse event:

Death of Subject	An event that results in the death of a subject.
Life-Threatening	An event that, in the opinion of the investigator, would have resulted in immediate fatality if medical intervention had not been taken. This does not include an event that would have been fatal if it had occurred in a more severe form.
Hospitalization or Prolongation of Hospitalization	An event that results in an admission to the hospital for any length of time or prolongs the subject's hospital stay. This does not include an emergency room visit or admission to an outpatient facility or hospitalization for respite care.
Congenital Anomaly	An anomaly detected at or after birth, or any anomaly that results in fetal loss.

Persistent or Significant Disability/Incapacity	An event that results in a condition that substantially interferes with the activities of daily living of a study subject. Disability is not intended to include experiences of relatively minor medical significance such as headache, nausea, vomiting, diarrhea, influenza, and accidental trauma (e.g., sprained ankle).
Important Medical Event Requiring Medical or Surgical Intervention to Prevent Serious Outcome	An important medical event that may not be immediately life-threatening or result in death or hospitalization, but based on medical judgment may jeopardize the subject and may require medical or surgical intervention to prevent any of the outcomes listed above (i.e., death of subject, life-threatening, hospitalization, prolongation of hospitalization, congenital anomaly, or persistent or significant disability/incapacity). Additionally, any elective or spontaneous abortion or stillbirth is considered an important medical event. Examples of such events include allergic bronchospasm requiring intensive treatment in an emergency room or at home, blood dyscrasias or convulsions that do not result in inpatient hospitalization, or the development of drug dependency or drug abuse.

For serious adverse events with the outcome of death, the date and cause of death will be recorded on the appropriate case report form. Deaths related to disease progression will not be recorded as adverse events.

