Of the 25 subjects enrolled across all doses at the 28 November 2015 data cut, the most common adverse events were nausea (68.0%), anemia (52.0%), and febrile neutropenia (36.0%). Events grade 3 and above were reported for all but one subject (96.0%); the most common event was anemia (48.0%). Serious adverse events were reported for 19 (76.0%) subjects, including febrile neutropenia (7 subjects), pyrexia, hyponatremia, and malignant neoplasm progression (2 subjects each). All other events occurred in one subject each. Fatal adverse events occurred in 5 (20.0%) subjects: 2 events of malignant neoplasm progression and one event each of acute hepatic failure, Candida pneumonia, and lung infection.

Additional safety and efficacy data are described in more detail in the current version of the Investigator's Brochure.⁹

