6.1.1.3 Adverse Events Expected due to Study Related Endpoints

Disease progression is an endpoint of this study. Disease progression should not be reported as an adverse event.

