6.1.1.3.1 Deaths

For this protocol, overall survival is an efficacy endpoint. Deaths that occur during the protocol specified adverse event collection period (Section 6.1.4) that are attributed by the investigator solely to progression of AML should be recorded only on the Death eCRF and the Study Completion Form eCRF. All other deaths during the protocol specified

adverse event collection period, regardless of relationship to study drug, must be recorded on the Adverse Event eCRF and Death eCRF and immediately reported to the Sponsor (Section 6.1.5). All deaths occurring after adverse event collection period should be collected in Death eCRF.

Death should be considered an outcome and not a distinct event. The event or condition that caused or contributed to the fatal outcome should be recorded as the single medical concept on the Adverse Event eCRF. Generally, only one such event should be reported. The term "sudden death" should only be used for the occurrence of an abrupt and unexpected death due to presumed cardiac causes in a patient with or without pre-existing heart disease, within one hour of the onset of acute symptoms or, in the case of an unwitnessed death, within 24 hours after the patient was last seen alive and stable. If the cause of death is unknown and cannot be ascertained at the time of reporting, "unexplained death" should be recorded on the Adverse Event eCRF. If the cause of death later becomes available (e.g., after autopsy), "unexplained death" should be replaced by the established cause of death.

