6.1.4 Adverse Event Collection Period

[figure not shown]
All protocol-related serious adverse events and nonserious adverse events must be collected from the signing of the study specific informed consent until study drug administration.

Serious and nonserious adverse events occurring after the study-specific informed consent is signed but prior to the initial dose of venetoclax/placebo, or LDAC will be collected only if they are considered by the Investigator to be causally related to the study-required procedures.

In addition, all serious and nonserious adverse events reported from the time of study drug administration until 30 days following discontinuation of study drug administration have elapsed will be collected, whether elicited or spontaneously reported by the subject.

Adverse event information will be collected as shown in [Figure 2](#).

Figure 2. Adverse Event Collection

* Only if considered by the Investigator to be causally related to study-required procedures.

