- Any treatment-emergent adverse event leading to LDAC reduction.
- Any treatment-emergent adverse event leading to death.

In addition, the treatment emergent AEs and serious AEs for selected grouped preferred terms (PTs) including, but not limited to, those listed in [Table 9](#), will be summarized.

Table 9. Selected Adverse Events

Selected Adverse Events	Search Criteria
Tumor Lysis Syndrome (AE)	SMQ – "Tumor Lysis Syndrome" (narrow)
Grade \geq 3 neutropenia	PT terms – "neutropenia," "neutrophil count decreased," "febrile neutropenia," "agranulocytosis," "neutropenic infection," and "neutropenic sepsis"
Grade \geq 3 infection, including opportunistic infections	SOC of "infections and infestations"
Haemorrhages	SMQ – "Haemorrhages" (narrow)
Anemia	PT terms – "Anaemia" and "Haemoglobin decreased"
Thrombocytopenia	PT terms – "Thrombocytopenia" and "Platelet count decreased"

There will be no statistical comparison for TEAEs between two treatment arms.

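### Protocol 6.1.1.2 and 6.1.1.3.1 give opposite recording rules for a death related to AML progression that also has another contributing cause

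*Protocol*

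**What the plan says.** Two current sections of the protocol set the recording rule for deaths.

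- **Protocol 6.1.1.2 (Serious Adverse Events)**, which lists what must reach the sponsor within 24 hours, ends with: "Deaths related to disease progression will not be recorded as adverse events". The sentence carries no sole-cause condition, no time window and no reference to another section.
- **Protocol 6.1.1.3.1 (Deaths)** says that deaths in the collection period "attributed by the investigator solely to progression of AML should be recorded only on the Death eCRF" and the study completion form. All other deaths in that period, "regardless of relationship to study drug, must be recorded on the Adverse Event eCRF and Death eCRF and immediately reported to the Sponsor". It adds: "The event or condition that caused or contributed to the fatal outcome should be recorded as the single medical concept on the Adverse Event eCRF".

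Between them, Protocol 6.1.1.3 says "Disease progression should not be reported as an adverse event". That deals with progression itself and not with a death that has more than one cause. Protocol 6.1.4 collects "all serious and nonserious adverse events reported from the time of study drug administration until 30 days following discontinuation of study drug administration".

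On the analysis side, SAP 11.1 includes a summary row for "Any treatment-emergent adverse event leading to death". SAP 11.2 separately counts all deaths, by timing relative to first and last dose. The SAP has no rule of its own for deaths of mixed cause.

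**The concern.** *Related to* progression is a wider class than *solely due to* progression. A death in the gap between the two, such as sepsis or hemorrhage in a subject whose AML is progressing, meets two opposite instructions. A site working from 6.1.1.2 may complete only the Death eCRF. A site working from 6.1.1.3.1 records a fatal adverse event and reports it at once.

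At stake is the consistency of the fatal adverse event data: the SAP 11.1 row, the immediate reports to the sponsor, and the adverse event data in the IDMC's periodic unblinded safety reviews (SAP 4.4). The class is realistic. Protocol 6.1.7 names infection and bleeding as complications of myelosuppression, and says it is unknown whether the events reported with LDAC came from treatment or from the underlying AML. If the arms differ in how often death is related to progression, the loss could also differ by arm.

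**Working it through.** The plan states no figure on this point, so the main check applies each rule to each kind of death in the collection period.

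| Cause of death | Protocol 6.1.1.2 | Protocol 6.1.1.3.1 | Result |
|---|---|---|---|
| Solely AML progression | Not an adverse event | Not on the Adverse Event eCRF | Agree |
| Related to progression, with another contributing cause | Not an adverse event | Adverse Event eCRF and immediate reporting | **Conflict** |
| Unrelated to progression | Not excluded | Adverse Event eCRF and immediate reporting | Agree |

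After the collection period, 6.1.1.3.1 asks only for the Death eCRF, so no conflict arises there. The contradiction is confined to the middle row.

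**What depends on the rule.** The fatal outcome decides whether the event is grade 5 (Protocol 6.1.2) and whether it enters the SAP 11.1 row for events leading to death.

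**What does not.** Under 6.1.1.3.1 every death goes on the Death eCRF, whatever its cause or timing. Overall survival (SAP 10.2.1) includes all deaths, and SAP 11.2 counts deaths without reference to adverse event coding.

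**Can a size be given?** The nearest figure is from Study M14-387 in Protocol 3.0: "Fatal adverse events occurred in 5 (20.0%) subjects". Two of the five were malignant neoplasm progression, which leaves 3/25 = 12% with another event. The text does not say whether any of those three was related to progression, so between 0 and 3 of them could fall in the conflicting class.

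For illustration, take 12% as the true rate in both arms: 0.12 × 140 = 16.8 and 0.12 × 70 = 8.4 deaths. Let *f* be the share related to progression in an arm, and *a* the share of those that sites leave off under 6.1.1.2. The recorded rate is 12% × (1 − *a* × *f*). Both *a* and *f* are assumptions.

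| *a* | *f*, venetoclax | *f*, control | Recorded, venetoclax v control |
|---|---|---|---|
| 0 | any | any | 12% v 12% |
| 1 | 1/2 | 1/2 | 6% v 6% |
| 1/2 | 1/3 | 2/3 | 10% v 8% |
| 1 | 1/3 | 2/3 | 8% v 4% (11.2/140 v 2.8/70) |
| 1 | 2/3 | 1/3 | 4% v 8% |

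The apparent difference runs from none to 4 percentage points in either direction, driven wholly by *a* and *f*. The 12% is itself weak: 25 subjects in an uncontrolled study, across all doses, applied here to a control arm as well.

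**The case against.** The strongest reply has three parts.

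1. **The event itself is still collected.** Protocol 6.1.1.2 excludes deaths, not infections or bleeds. Section 6.1.1.3.1 treats death as an outcome and not an event. Sepsis or hemorrhage in the window is an adverse event under 6.1.1.1, is collected under 6.1.4, and will often be serious on another ground such as hospitalization. The sentence just before the one at issue also presupposes that serious adverse events with a fatal outcome are recorded. This largely stands. A reader might infer that such events never reach the sponsor, and the documents do not support that. What remains open is whether the fatal outcome is attached to the event, which is what the SAP 11.1 row needs.

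2. **The specific section governs.** Section 6.1.1.3.1 is headed for deaths, names the forms and uses mandatory wording. This is a sensible reading, but the protocol does not state it, and 6.1.1.2 is a section that a site could apply alone when deciding what to report within 24 hours.

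3. **Safeguards limit the harm.** SAP 11.1 has its own rows for grade 3 or higher infection and for hemorrhage, and plans no statistical comparison of treatment-emergent events. SAP 11.2 counts every death. This stands, and it keeps the point to the fatal-event row, reporting and safety review.

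A reader might also take any fatal infection in a subject with active AML to be excluded. The trigger in 6.1.1.2 is progression, and Protocol 5.3.3 separates resistant from progressive disease. A fatal infection with persistent but non-progressing AML is not excluded merely because leukemia is present.

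**Conclusion.** The two sections contradict each other for one class of death: within the collection period, related to progression, but not solely due to it. For that class, whether a fatal outcome is coded and reported can vary by site, and with it the SAP 11.1 row for events leading to death and the adverse event data the IDMC sees. Overall survival and total death counts do not change.

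A reader might infer a bias against venetoclax of known size, on the reasoning that better disease control leaves more control-arm deaths related to progression and so more of them unrecorded. That direction is possible, but the documents do not give the share of mixed-cause deaths in either arm or the rule that sites followed. The difference vanishes when the shares are equal and reverses when they are swapped. Nor do the documents say that mixed-cause deaths are common. The textual conflict is certain; its effect on the comparison cannot be sized.

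**What to change.** **Protocol text.** Replace the sentence in 6.1.1.2 with the standard in 6.1.1.3.1: only deaths in the collection period that the investigator attributes solely to AML progression stay off the Adverse Event eCRF. Cross-reference 6.1.1.3.1, and keep its rule that the causing or contributing condition is entered as a single medical concept, generally one event per death.

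**Data.** Protocol 1.1 records that the final analysis is complete, so new wording cannot correct what has already been analyzed. Query Death eCRF entries in the collection period that list progression together with another contributing cause and have no matching fatal adverse event. If any are found, update the summary of treatment-emergent events leading to death.

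**Cost.** One sentence, a query limited to collection-period deaths with that pattern, a rerun of the fatal-event summary if needed, and slightly more serious adverse event reports.
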